The protocol can be stopped at any moment for safety considerations during the 8-h study period if the attending intensivist considers that the patient has developed unexpected and severe complications or evolves into refractory shock, conditions that under his judgment require liberalization of management. This action has to be reported on the case report form (CRF), and the patient will be followed up with major outcomes, and included in the intention-to-treat (ITT) analysis. Specific safety measures for fluid administration, vasopressor test and inodilator use are specified above.

Suspected unexpected serious adverse reactions (SUSAR)

Any adverse event that occurs in a clinical trial subject, which is assessed by the study investigator as being unexpected, serious and as having a reasonable possibility of a causal relationship with the study procedure will be reported. Reports of these reactions are subject to expedited submission to health authorities. SUSAR's will be analyzed by both the SCC and the data safety monitoring committee (DSMC).

Blinding

Since the intervention will be administered to critically ill patients (mostly sedated), blinding of these patients is not necessary. Because this is a non-pharmacological intervention, blinding of the medical team is not feasible.

Data collection and management

Study follow-up and the variables that will be collected are described below.

Baseline

Demographics, comorbidities, acute physiology and chronic health evaluation (APACHE) II [31], sepsis source and treatment

pre-ICU resuscitation and fluid balance

Sequential Organ Failure Assessment (SOFA) [26] + and Acute Kidney Injury Network (AKI) criteria [32]

Hemodynamics: HR, SBP, diastolic blood pressure (DBP), MAP, CVP, FR status, intraabdominal pressure (IAP), NE levels, diuresis.

Perfusion: lactate, central venous O₂ saturation (ScvO₂), central venous arterial pCO₂ gradient (P(cv-a)CO₂), Hb, central venous and arterial blood gases, CRT, mottling score.

Evolution

SOFA and AKI criteria at 8, 24, 48 and 72 h

Hemodynamics hourly up to 8 h

Fluid administration and balance at 8, 24, 48 and 72 h

Complete perfusion assessment when the targeted parameter is normalized and then at 8, 24, 48 and 72 h

Register of vasoactive drugs and dobutamine/milrinone use

Register of MV and RRT

Source control re-analysis at 4 h

Rescue therapies: HVHF, vasopressin, epinephrine, steroids, others.

Echocardiography at least once during the study period

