- In-hospital mortality, truncated at 90 days.

The protocol did not call for systematic measurement of intra-abdominal pressure.

Therefore, intra-abdominal pressure was measured according to physicians' discretion when they suspected of intra-abdominal hypertension.

Analysis methods

Continuous distribution will be assessed by visual inspection of histograms and D'Agostino-Pearson's normality tests. Variables will be expressed as counts and percentages, mean and standard deviation (SD), or median and interquartile range (IQR), whenever appropriate, as indicated in mock tables 1 to 3, which we intend to include in the main results paper.

The evolution of hemodynamic and perfusion variables in both groups during the study will be presented as in mock table 2. We will carry out linear mixed models for continuous variables where Gaussian error distribution applies to account for the repeated measurements on the same patient. Binary variables will be tested using logistic mixed regression models and continuous variables with non-symmetrical distributions such as Lactate and Mottling score will use the distribution that best fit the data.

We will assess the effect of PPTR versus LTR on the primary outcome using Cox proportional hazards models, with adjustment for 5 pre-specified baseline covariates: APACHE II score, SOFA score, lactate level, CRT and source of infection, as fixed

(individual-level) effects. Results will be reported as hazard ratios with 95% confidence intervals (CI) and P-values. We should also present Kaplan Meier curves.

Effects on secondary and tertiary outcomes will be presented as hazard ratio for 90-day all-cause mortality and renal replacement therapy within 28 days, or risk difference for all other binary outcomes, along with 95% CI and P-values (calculated with Fisher's exact tests), as shown in mock table 3. The effect on 90-day all-cause mortality and the need of renal replacement therapy within 28 days will be assessed with Cox-proportional hazard model without adjustment for baseline covariates.

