We will estimate the effect on mechanical ventilation-free days, renal replacement therapy-free days and vasopressors-free days within 28 days with generalized linear models using the distribution that better fits the data (possibly truncated Poisson distribution). Effects on organ dysfunction at 72 hours (measured by SOFA) will be calculated with generalized linear models with the distribution that better fits the data with adjustment for the baseline SOFA. Effect on other continuous outcomes, such as ICU or hospital length of stay, amount or resuscitation fluids, fluid balance, will also be calculated with generalized linear models with the distribution that better fits the data (normal, gamma, inverse Gaussian, or other), without adjustment for covariates.

Subgroup analyses

We will use Cox proportional hazards adjusted for baseline covariates (same as main analysis) to assess interactions between treatment effect and the following prespecified subgroups: a) Patients with lactate > 4.0 mmol/L versus equal or lower than 4 mmol/L; b) Patients without a confirmed source of infection (as this could increase the translation of

the study to other critically ill) versus those with confirmed source of infection; c) Patients with APACHE II lower versus equal or higher than 25; d) Patients with SOFA score lower versus equal or higher than 10; e) Patients with a more than 10% difference in lactate levels between the very first one measured and the baseline when starting the study.

Sensitivity analysis

We will assess the effect of PPTR compared to LTR on 28-day mortality using a frailty Cox model with site as random effect and adjustment for the same baseline co-variables as in the main analysis (APACHE II score, SOFA score, lactate level, CRT and source of infection).

Harms

Our primary, secondary and tertiary outcomes are intended to reflect potential harms resulting from the PPTR versus LTR approach for managing septic shocks.

Missing data

Primary outcome (28-day mortality) will be treated as time to event outcome and reported as Cox proportional hazard models, patients with loss of follow up will be censored in the last contact. We will use multiple imputation methods to assess treatment effect on the primary outcome if there are cases without no follow-up information at all. As a sensitivity analysis, we will also assess the effect on the primary outcome using complete case data.

Statistical software

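### The SAP names no baseline covariate for the ventilation-, RRT- and vasopressor-free-day models; read as unadjusted, they are valid but give up precision that severity data already collected could supply

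*SAP*

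**What the plan says.** The SAP, under Analysis methods, gives each group of outcomes its own model.

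- **Primary outcome:** a Cox model "with adjustment for 5 pre-specified baseline covariates: APACHE II score, SOFA score, lactate level, CRT and source of infection".
- **90-day mortality and need for RRT within 28 days:** Cox models, stated to be unadjusted.
- **The three free-day outcomes:** "We will estimate the effect on mechanical ventilation-free days, renal replacement therapy-free days and vasopressors-free days within 28 days with generalized linear models", with whichever distribution fits better, possibly a truncated Poisson. Nothing is said about covariates, either way.
- **SOFA at 72 hours:** a generalized linear model "with the distribution that better fits the data with adjustment for the baseline SOFA".
- **Other continuous outcomes, such as lengths of stay and fluids:** generalized linear models ("normal, gamma, inverse Gaussian, or other), without adjustment for covariates".

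Mock Table 3 reports the three free-day outcomes as mean differences. The protocol's short plan for continuous secondary outcomes (t test, or bootstrapped difference in medians) also names no covariate. The only planned sensitivity analyses concern 28-day mortality.

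All five covariates are available. The protocol's Baseline list under Data collection and management includes "Demographics, comorbidities, acute physiology and chronic health evaluation (APACHE) II [31], sepsis source and treatment", and further down that list SOFA, lactate and CRT. The SAP's Randomization section says that allocation is not stratified. Its section on confidence intervals and P values says that secondary results are to be read as exploratory.

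**The concern.** The free-day outcomes carry part of the secondary objective in both documents. They count days free of organ support, and SOFA is an organ-failure score, so baseline severity can reasonably be expected to predict them. The sponsor already treats the five covariates as worth adjusting for in the primary, subgroup and frailty models. Leaving them out of the free-day models widens those intervals for no saving in data collection.

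The silence has a cost of its own. The neighbouring sentences say whether they adjust and this one does not, so the covariate set could be settled after results are seen. The SAP says it exists to prevent that kind of choice.

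**Working it through.** **1. The plan's own power figure.** The only stated power is for 28-day mortality: about 90% with 210 per group, 45% versus 30%, two-sided alpha 5%. A two-proportion calculation gives 89.1%. A log-rank (Schoenfeld) calculation with HR = ln(0.70)/ln(0.55) = 0.597 and 420 × 0.375 = 157.5 deaths gives 90.0%. The figure reproduces, but it does not bear on free days, for which the documents state no target effect, power or precision.

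**2. Inputs for free days.** 210 per group and alpha 5% come from the SAP. Two inputs are assumed: the correlation rho between the covariates and the outcome, and the unadjusted power used as a reference point.

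**3. Formula.** In a linear model, adjustment multiplies the variance of the treatment difference by about 1 − rho². Power after adjustment is Φ[(1.96 + z_base)/√(1 − rho²) − 1.96], where z_base is 0.842 for 80% and 0.524 for 70%. Worked at rho = 0.4 from 80%: (1.96 + 0.842)/√0.84 = 3.057; 3.057 − 1.96 = 1.097; Φ = 86.4%. The equivalent total sample size is 420/(1 − rho²).

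| rho | variance factor | equivalent N (extra) | power from 80% | power from 70% |
|---|---|---|---|---|
| 0.2 | 0.96 | 438 (18) | 81.6% | 71.8% |
| 0.3 | 0.91 | 462 (42) | 83.6% | 74.0% |
| 0.35 | 0.88 | 479 (59) | 84.9% | 75.6% |
| 0.4 | 0.84 | 500 (80) | 86.4% | 77.4% |
| 0.5 | 0.75 | 560 (140) | 89.9% | 81.8% |

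The gain is about 5 points at rho 0.35 and smaller below that. At rho 0.5 the interval narrows by 1 − √0.75 = 13%.

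**4. Chance imbalance.** With 210 per group, a severity difference of one standard error is √(2/210) = 0.098 SD. At rho 0.4 it moves the unadjusted result by 0.4 × 0.098 = 0.04 SD. The effect with 80% power is (1.96 + 0.842) × 0.098 = 0.273 SD, so the shift is about one seventh of it. This is ordinary sampling error, already covered by a correct standard error.

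**5. Does the formula carry over to the planned models?** Free days were simulated for 420 patients with about 38% zeros, mean 12 and SD 10.5. These values are assumptions; the SAP does not say how deaths enter the free-day count.

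- **Linear model:** the ratio of adjusted to unadjusted variance was 0.97, 0.91, 0.88, 0.80 and 0.71 at correlations of about 0.18, 0.28, 0.36, 0.46 and 0.55, close to 1 − rho².
- **Plain Poisson model, model-based standard errors:** adjustment did not reduce the reported standard error (ratio about 1.00), and a true null was rejected in about 50% of runs because the data are overdispersed.
- **Plain Poisson model, robust standard errors:** the gain appeared (ratio of about 0.91 at a correlation of about 0.41), and rejection of a true null fell to between about 5% and 10% across runs.

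The simulation used a plain Poisson model. The SAP mentions a truncated Poisson only as a possibility, so this shows a risk to guard against, not what the trial will do.

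**The case against.** The strongest reply is that nothing here is an error. An unadjusted comparison of randomized groups is valid, secondary results are exploratory, and no power is promised for free days. A reader might infer that unstratified randomization lets severity imbalance bias these outcomes, or that they could diverge from the adjusted primary result only through such imbalance. The documents support neither inference. Chance imbalance is part of sampling error, and these are different outcomes on a different scale, which can differ from mortality for many reasons.

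A reader might also take it that the SAP declares these models unadjusted. It does not; that is inferred from silence. The inference is likely, given the protocol's unadjusted methods and the SAP's treatment of 90-day mortality and lengths of stay, but it is still an inference.

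The SAP may also be following a policy: adjust the primary outcome, leave the others unadjusted, and adjust 72-hour SOFA only for its own baseline value. Free days have no baseline value, so that precedent does not transfer directly. This stands as a possible explanation, but the SAP does not state it for free days. The precision argument also applies to 90-day mortality and lengths of stay; the difference is that the SAP makes its choice explicit there.

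Finally, the correlation is assumed, and a single value is applied to three outcomes. Eligibility may lower it: every patient needs vasopressors, while severe ARDS and anticipated early dialysis are excluded, which narrows the range of severity. This stands, and it is why the size is given only as a range.

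**Conclusion.** The point holds as a matter of efficiency. The SAP names no covariate for the three free-day models, and the likely unadjusted analysis is valid but less precise than the collected data allow. If 80% is taken as the unadjusted power, adjustment brings about 82% at rho 0.2, 84% at 0.3, 86% at 0.4 and 90% at 0.5. That is worth about 18 to 140 extra patients on 420. At rho of 0.2 or less it is negligible.

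These figures rest on an assumed correlation, an assumed reference power, and a variance estimated from the data and not fixed by a Poisson assumption. The documents do not support a claim of bias, of lost stated power, or of any effect on the primary result. The change is desirable, not essential.

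**What to change.** In the SAP's Analysis methods, state that each free-day model adjusts for the five covariates of the primary model, or at minimum for baseline SOFA and APACHE II. Report the covariate-standardised (marginal) mean difference, so that the mean-difference entry in mock Table 3 keeps its meaning under any link function. Use a robust (sandwich) or bootstrap standard error, since model-based Poisson errors would hide the gain and understate uncertainty when there are many zeros. Show the unadjusted difference beside it. If the sponsor prefers no adjustment, say so explicitly, as is done for the other outcomes.

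The cost is a few lines of SAP text before database lock, slightly more code for standardisation and its standard error, and a simple rule for missing baseline covariates. The SAP's Missing data section covers only the primary outcome and does not mention covariates, and the adjusted primary model needs such a rule as well. No new data are required.

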Monitoring peripheral perfusion is particularly attractive because of its easy clinical accessibility and more importantly, because it could reflect the adequacy of intraabdominal visceral organ perfusion [16, 17]. The skin territory lacks auto-regulatory flow control, and therefore, sympathetic activation impairs skin perfusion during circulatory dysfunction [17], a phenomenon that could be evaluated by peripheral perfusion assessment. A robust body of evidence confirms that abnormal peripheral perfusion after initial resuscitation is associated with increased morbidity and mortality [18–23], whereby it could be used as a potential resuscitation goal [24]. In fact, the presence of a cold clammy skin, mottling or prolonged capillary refill time (CRT) has been suggested as indicators to initiate fluid resuscitation in patients with septic shock [17]. Interestingly, CRT was the first parameter to be normalized in patients surviving from septic shock and predicted lactate normalization at 24 h [18]. A recent pilot study suggests that targeting peripheral perfusion during septic shock resuscitation is safe and associated with less fluid administration and organ dysfunctions [25]. Therefore, the excellent prognosis associated with CRT recovery, its rapid-response time to fluid loading, its relative simplicity, its availability in resource-limited settings and its capacity to change in parallel with perfusion of physiologically relevant territories such as the hepatosplanchnic region [16] constitute strong reasons to evaluate the usefulness of CRT to guide resuscitation in septic shock patients.

Consequently, we decided to conduct a randomized controlled trial (RCT) comparing peripheral

perfusion-targeted resuscitation (PPTR) versus lactate-targeted resuscitation (LTR) in patients with septic shock, hypothesizing that resuscitation aimed at peripheral perfusion will be associated with lower mortality rates. We also hypothesize that patients assigned to PPTR will require less volume of fluids with subsequent lower positive fluid balances. Accordingly, PPTR should be associated with less organ dysfunctions, especially at respiratory, renal and gastrointestinal levels.

Methods

Primary objective

To determine if PPTR is associated with lower mortality rates at 28 day than a LTR in patients with septic shock.

Secondary objectives

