Consecutive adult patients (≥ 18 years) with septic shock admitted to the intensive care unit will be considered eligible. Septic shock is defined as suspected or confirmed infection, plus hyperlactatemia (≥ 2.0 mmol per liter) and vasopressor requirements due to refractory hypotension.¹⁰ This latter is characterized as a systolic blood pressure (SBP) < 90 mmHg or a mean arterial pressure (MAP) < 65 mmHg after an intravenous fluid load of at least 20 ml/kg, administered over the course of 60 minutes.

Patients will be excluded in case of:

- pregnancy;
- anticipated surgery or dialysis procedure during the first 8 hours after septic shock diagnosis;
- Do-not-attempt-resuscitation status;
- active bleeding;
- acute hematological malignancy;
- concomitant severe acute respiratory distress syndrome (ARDS);
- more than 4h after the onset of septic shock criteria.

Recruitment

Information that will be included in the CONSORT flow diagram is shown in Fig 2.

Withdrawal/follow-up

We will tabulate the number of patients whose consent for trial participation is withdrawn either by the patient or his or her legal representative. When consent is withdrawn for trial

participation we will nevertheless attempt to obtain consent for collecting and analyzing follow-up data. These cases should also be reported.

Baseline patient characteristics

The baseline characteristics to be registered during the trial will be presented as in mock table 1.

ANALYSIS

Outcome definitions

Our primary outcome is all-cause mortality within 28 days.

Our secondary outcomes are:

- All-cause mortality within 90 days;
- Mechanical ventilation-free days during the first 28 days after randomization. A day free of mechanical ventilation is defined as no need of invasive mechanical ventilation in any time during a given day;
- Renal replacement therapy-free days during the first 28 days after randomization;
- Vasopressor-free days during the first 28 days after randomization;
- Organ dysfunction assessed with the Sepsis-related Organ Failure Assessment (SOFA) score at 72 hours after randomization;¹⁵
- ICU and hospital lengths of stay, truncated at 90 days;

Our tertiary exploratory outcomes are:

- Amount of resuscitation fluids in the first 8 and 24 hours after randomization;
- Total fluid balance in the first 8, 24, 48 and 72 hours;

- Occurrence of intra-abdominal hypertension (IAH) during the first 72 hours after randomization (%).
- Use of RRT (%) within 28 days;

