Hemodynamic and perfusion-related variables		
Heart rate, mean (SD), bpm	xx.x (xx.x)	xx.x (xx.x)
Mean arterial pressure, mean (SD), mmHg	xx.x (xx.x)	xx.x (xx.x)
Norepinephrine dose, mean (SD), mcg/kg/min	x.xx (x.xx)	x.xx (x.xx)
Central venous pressure, mean (SD), mmHg	xx.x (xx.x)	xx.x (xx.x)
Serum lactate, mean (SD), mmol/L	x.xx (x.xx)	x.xx (x.xx)
Central venous oxygen saturation, mean (SD), %	xx.x (xx.x)	xx.x (xx.x)
Venous-arterial pCO2 gradient, mean (SD), mmHg	xx.x (xx.x)	xx.x (xx.x)
Capillary refilling time, median (IQR), sec	x (x to x)	x (x to x)
Mottling score, median (IQR)	x (x to x)	x (x to x)
Initial management data		
Time from matching entry criteria to randomization, mean (SD), min.	xx (xx)	xx (xx)
Intravenous fluid loading before randomization, mean (SD), mL	xxxx (xxxx)	xxxx (xxxx)
Time from diagnosis of septic shock to first antibiotics, mean (SD), min.	xxx (xxx)	xxx (xxx)

Abbreviations: SD, standard deviation; IQR, interquartile range; bpm, beats per minute; SOFA, Sequential Organ Failure Assessment; APACHE, Acute physiology and chronic health evaluation.

Table 2. Evolution of Hemodynamic and Perfusion Variables from Baseline to 72 hours in the peripheral perfusion-targeted resuscitation (PPTR) and lactate-targeted resuscitation (LTR) groups

Variable	Group	Basal	2h	4h	8h	24h	48h	72h
Number of patients	PPTR	xxx	xxx	xxx	xxx	xxx	xxx	xxx
	LTR	xxx	xxx	xxx	xxx	xxx	xxx	xxx
Heart rate, mean, bpm	PPTR	xxx	xxx	xxx	xxx	xxx	xxx	xxx
	LTR	xxx	xxx	xxx	xxx	xxx	xxx	xxx
	P-value	-	x.xx	x.xx	x.xx	x.xx	x.xx	x.xx
Systolic blood pressure, mean, mmHg	PPTR	xxx	xxx	xxx	xxx	xxx	xxx	xxx
	LTR	xxx	xxx	xxx	xxx	xxx	xxx	xxx
	P-value	-	x.xx	x.xx	x.xx	x.xx	x.xx	x.xx
Diastolic blood pressure, mean, mmHg	PPTR	xx	xx	xx	xx	xx	xx	xx
	LTR	xx	xx	xx	xx	xx	xx	xx
	P-value	-	x.xx	x.xx	x.xx	x.xx	x.xx	x.xx
Mean arterial pressure, mean, mmHg	PPTR	xx	xx	xx	xx	xx	xx	xx
	LTR	xx	xx	xx	xx	xx	xx	xx
	P-value	-	x.xx	x.xx	x.xx	x.xx	x.xx	x.xx
Norepinephrine dose, mean, mcg/Kg/min	PPTR	x.xx	x.xx	x.xx	x.xx	x.xx	x.xx	x.xx
	LTR	x.xx	x.xx	x.xx	x.xx	x.xx	x.xx	x.xx
	P-value	-	x.xx	x.xx	x.xx	x.xx	x.xx	x.xx
Norepinephrine use, no. (%)	PPTR	xx (xx.x)	xx (xx.x)	xx (xx.x)	xx (xx.x)	xx (xx.x)	xx (xx.x)	xx (xx.x)
	LTR	xx (xx.x)	xx (xx.x)	xx (xx.x)	xx (xx.x)	xx (xx.x)	xx (xx.x)	xx (xx.x)
	P-value	-	x.xx	x.xx	x.xx	x.xx	x.xx	x.xx

Diuresis, mean, total mL in previous period	PPTR	-	xxx	xxx	xxx	xxx	xxx	xxx
	LTR	-	xxx	xxx	xxx	xxx	xxx	xxx
	P-value	-	x.xx	x.xx	x.xx	x.xx	x.xx	x.xx

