Lactate, mean, mmol/L	PPTR	x.xx	x.xx	x.xx	x.xx	x.xx	x.xx	x.xx
	LTR	x.xx	x.xx	x.xx	x.xx	x.xx	x.xx	x.xx
	P-value	-	x.xx	x.xx	x.xx	x.xx	x.xx	x.xx
Capillary refill time, median, sec	PPTR	x	x	x	x	x	x	x
	LTR	x	x	x	x	x	x	x
	P-value	-	x.xx	x.xx	x.xx	x.xx	x.xx	x.xx
Central venous oxygen saturation, mean, %	PPTR	xx	-	-	xx	xx	xx	xx
	LTR	xx	-	-	xx	xx	xx	xx
	P-value	-	-	-	x.xx	x.xx	x.xx	x.xx
Delta PaCO ₂ , mean, mmHg	PPTR	xx.x	-	-	xx.x	xx.x	xx.x	xx.x
	LTR	xx.x	-	-	xx.x	xx.x	xx.x	xx.x
	P-value	-	-	-	x.xx	x.xx	x.xx	x.xx
Mottling score, median	PPTR	x	-	-	x	x	x	x
	LTR	x	-	-	x	x	x	x
	P-value	-	-	-	x.xx	x.xx	x.xx	x.xx

Abbreviations: Delta PaCO₂, central venous-arterial pCO₂ gradient

Table 3. Outcomes of Patients Treated with Peripheral Perfusion-Targeted Resuscitation versus Lactate-Targeted Resuscitation

Outcome	Peripheral perfusion-targeted resuscitation (n=xxx)	Lactate-targeted resuscitation (n=xxx)	Type of effect estimate	Effect estimate (95% CI)	P Value
Primary Outcome					
Death within 28 days, no. (n%)	xx (xx.x)	xx (xx.x)	Hazard ratio	x.xx (x.xx to x.xx)	x.xx
Secondary Outcomes					
Death within 90 days, no. (n%)	xx (xx.x)	xx (xx.x)	Hazard ratio	x.xx (x.xx to x.xx)	x.xx
Mechanical ventilation-free days within 28 days, mean (SD)	xx.x	xx.x	Mean difference	x.x (x.x)	x.xx
Renal replacement therapy-free days within 28 days, mean (SD)	xx.x	xx.x	Mean difference	x.x (x.x)	x.xx
Vasopressor-free days within 28 days, mean (SD)	xx.x	xx.x	Mean difference	x.x (x.x)	x.xx
SOFA, mean (SD)					
SOFA at 8h	x.x	x.x	Mean difference	x.x (x.x)	x.xx
SOFA at 24h	x.x	x.x	Mean difference	x.x (x.x)	x.xx
SOFA at 48h	x.x	x.x	Mean difference	x.x (x.x)	x.xx
SOFA at 72h	x.x	x.x	Mean difference	x.x (x.x)	x.xx
ICU length of stay, mean (SD), d	x.x	x.x	Mean difference	x.x (x.x)	x.xx
Hospital length of stay, mean (SD), d	x.x	x.x	Mean difference	x.x (x.x)	x.xx
Tertiary Outcomes					
Amount Resuscitation fluids, mean (SD), mL					
At 8 h	xxxx (xxxx)	xxxx (xxxx)	Mean difference	xxx (xxx to xxx)	x.xx
At 24 h	xxxx (xxxx)	xxxx (xxxx)	Mean difference	xxx (xxx to xxx)	x.xx
Total fluid balance, mean (SD), mL					
At 8 h	xxxx (xxxx)	xxxx (xxxx)	Mean difference	xxx (xxx to xxx)	x.xx
At 24 h	xxxx (xxxx)	xxxx (xxxx)	Mean difference	xxx (xxx to xxx)	x.xx
At 72 h	xxxx (xxxx)	xxxx (xxxx)	Mean difference	xxx (xxx to xxx)	x.xx

Intra-abdominal hypertension, no. (%)	xx (x.x)	xx (x.x)	Risk difference	x.x (x.x to x.x)	x.xx
Use of renal replacement therapy, no. (%)	xx (x.x)	xx (x.x)	Risk difference	x.x (x.x to x.x)	x.xx

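### Fluid volume and fluid balance are compared without covariates although fluid before randomization is recorded: a modest, cheaply recovered loss of precision, plus a missing 48-h row in mock Table 3

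*SAP*

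**What the plan says.** The SAP (Analysis methods) groups the fluid outcomes with the lengths of stay: "Effect on other continuous outcomes, such as ICU or hospital length of stay, amount or resuscitation fluids, fluid balance". All of these are to be analysed by generalized linear models with the "distribution that better fits the data (normal, gamma, inverse Gaussian, or other), without adjustment for covariates". The sentence before it treats 72-h SOFA differently, "with adjustment for the baseline SOFA". The primary Cox model carries five baseline covariates: APACHE II, SOFA, lactate, CRT and source of infection.

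A measure of earlier fluid is available. Mock Table 1 of the SAP has the row "Intravenous fluid loading before randomization, mean (SD), mL", and the protocol's baseline data list includes "pre-ICU resuscitation and fluid balance".

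The protocol's Background hypothesizes that "patients assigned to PPTR will require less volume of fluids with subsequent lower positive fluid balances". The SAP's Sample size section also uses fluid limitation to argue that the assumed mortality effect is plausible.

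Among the tertiary exploratory outcomes the SAP lists "Total fluid balance in the first 8, 24, 48 and 72 hours". The protocol's outcome list gives the same four times, and its data collection section records balance at each of them. In mock Table 3, under "Total fluid balance, mean (SD), mL", there are rows for 8, 24 and 72 h only.

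**The concern.** Fluid is the pathway by which the plan expects one strategy to outperform the other, so readers will use the fluid rows to interpret whatever mortality result appears. Entry requires a minimum earlier fluid load with no stated maximum, and patients may enter at any time up to 4 h after onset, so earlier volume can vary between patients. Randomization uses permuted blocks without stratification, so nothing in the design balances earlier fluid or severity beyond chance.

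If earlier fluid or severity predicts later fluid, in either direction, an unadjusted comparison leaves that variation in the error term and any chance imbalance in the estimate. If Table 1 then showed unequal earlier fluid, adjusting at that stage would be a post hoc choice, which is what the SAP says it wants to avoid.

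The 48-h balance is a separate matter of consistency. The mock tables are intended for the main paper, and one of four prespecified time points has no place in them.

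**Working it through.** **The plan's own figure.** The only sample-size statement concerns 28-day mortality: 210 per group, 45% versus 30%, two-sided 5%, about 90% power. With pooled rate 0.375, the null SE is √(2 × 0.375 × 0.625 / 210) = 0.0472 and the alternative SE is √((0.45 × 0.55 + 0.30 × 0.70) / 210) = 0.0467. Then z = (0.15 − 1.96 × 0.0472) / 0.0467 = 1.23, a power of 89.1%. The figure reproduces and is not in dispute. No power or detectable difference is stated for the fluid outcomes.

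**Inputs for the fluid outcomes.** N = 420, 210 per group (SAP, Sample size). The share of outcome variance explained by baseline covariates (R²) is not in the documents; 1% to 20% is assumed.

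**Precision.** In a linear model, adjusted SE ≈ √(1 − R²) × unadjusted SE, and the equivalent number of extra patients is 420 × (1/(1 − R²) − 1).

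| Assumed R² | SE ratio | SE reduction | Equivalent extra patients |
|---|---|---|---|
| 1% | 0.995 | 0.5% | 4 |
| 5% | 0.975 | 2.5% | 22 |
| 10% | 0.949 | 5% | 47 |
| 20% | 0.894 | 11% | 105 |

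The difference detectable with 80% power is (1.96 + 0.842) × √(2/210) = 0.273 SD unadjusted. It becomes 0.273 × 0.995 = 0.272 SD at R² = 1% and 0.273 × 0.894 = 0.244 SD at R² = 20%.

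**Chance imbalance.** The SE of a baseline difference is √(2/210) = 0.098 SD, so a 1.96-SE imbalance is 0.19 SD. With correlation r between earlier fluid and the outcome, the unadjusted estimate shifts by r × 0.19 SD: 0.02 SD at r = 0.1 (R² = 1%) and 0.06 SD at r = 0.3 (R² = 9%).

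**Cost of the covariates.** Estimating q covariate coefficients inflates the variance by about q/(N − q − 3).
- Earlier fluid alone (q = 1): 1/416 = 0.24% of variance, about 0.1% of the SE. This is below the gain even at R² = 1%.
- Adding the five primary-model covariates, with source of infection in the six categories of mock Table 1: q = 1 + 4 + 5 = 10, and 10/407 = 2.5% of variance, about 1.2% of the SE. The net gain is then positive only if R² exceeds roughly 2.5%.

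This is why earlier fluid is the core covariate and the other five are optional.

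**Table 3.** Prespecified balance times: 8, 24, 48, 72 h (four). Rows in the table: 8, 24, 72 h (three). The three rows are intact and consecutive, so loss in text extraction looks unlikely.

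**The case against.** Most of the opposing case stands. Under 1:1 randomization the unadjusted comparison is unbiased on average, and its confidence interval already allows for chance imbalance. The choice is explicit and prespecified. It is also in keeping with the rest of the plan: the protocol's summary analyses of continuous outcomes are unadjusted, and so is the SAP's 90-day mortality analysis, a higher-ranked outcome. The fluid outcomes are labelled tertiary and exploratory. A narrow range of earlier fluid among patients who met the entry criteria could make its correlation with later fluid small. The square-root formula belongs to a linear model and does not carry over directly to the gamma or inverse Gaussian models that the SAP also permits.

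Earlier fluid is also not a baseline of the outcome in the way that baseline SOFA is: it is a different volume over a different window. The protocol's pre-ICU item and the SAP's before-randomization item need not be the same quantity either, since patients can develop shock during their ICU stay. This does not prevent its use as a covariate, but the variable must be named.

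Three stronger readings are tempting, and the documents do not support them. A reader might infer that the fluid outcomes are alone in leaving a related baseline unused. They are not: baseline norepinephrine dose and intra-abdominal pressure are on the protocol's baseline list, yet no adjustment is stated for vasopressor-free days or intra-abdominal hypertension. A reader might infer that the unadjusted analysis is biased or invalid; randomization rules that out. A reader might infer from Table 3 that the 48-h balance will go unreported. It remains defined, collected and covered by the stated model, and the table does not match the outcome list elsewhere either: it shows SOFA at 8, 24 and 48 h, although only 72 h is a listed outcome.

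**Conclusion.** The point holds as a missed, nearly free gain in precision on outcomes that carry the plan's mechanistic hypothesis. It is not an error of validity and does not bear on the primary result. The gain is a standard error about 0.5% to 11% smaller, if baseline covariates explain 1% to 20% of the variance. That range is an assumption, the true value could lie near its lower end, and the small cost of estimating the coefficients comes off it. The calculation also assumes a linear model for the mean difference and near-complete data on 420 patients. The missing 48-h row is a definite but minor inconsistency and adds no weight to the case for adjustment.

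**What to change.** Before database lock, amend the SAP's Analysis methods for resuscitation fluids (8, 24 h) and fluid balance (8, 24, 48, 72 h). In place of the no-covariate clause, specify a model for the mean difference adjusted for intravenous fluid before randomization as defined in mock Table 1. The five primary-model covariates may be added; whether they are in should be stated in advance. Show the unadjusted arm means beside the adjusted difference. A mean-difference model also matches the effect measure already named in Table 3, and it avoids gamma or inverse Gaussian models for balance, which can be zero or negative.

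Add the 48-h fluid-balance row to mock Table 3.

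The cost is SAP wording and one table row, with no new data. A few patients may lack a recorded earlier volume; a simple imputation rule, stated in advance, would cover them.
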